6.2 Clinical procedure

6.2.1 Screening:

The recruited XCS fulfilling the inclusion and avoided the exclusion criteria will be registered and asked to participate in the study. The athletes who are willing to sign the informed consent form will be enrolled in the study. During this one week the participants will undergo a clinical screening and an appointment for the starting visit in the study one week later. Before the first investigation, the participants will be asked to fill in their diet for four days in a data application created for this study. The diet registration will be performed and monitored by a nutritionist. All the athletes will be instructed not to change their usual intake of food during the study but change the usual used cheese with the study cheese. During this initial clinical examination, all demographic data, social factors, history of disease and vital signs will be recorded.

6.2.2: Start-up Day:

A clinical investigation with blood sampling will be performed at the start-up denoted as Day 0, and they are all asked to meet fastening, and without hard training two days in front. Blood samples will be collected for measurements of Osteocalcin, vitamin K₂; Biochemical variables like; Ca, Mg, Na, potassium, urea, phosphate, creatinine, ferritin, haemoglobin, HbA1C, Lipids, CTX-1, PINP, BALP, PTH, Estradiol, Testosterone, LH, FSH and vitamin D. Additionally, DXA investigation of BMD and TBS, FFM and LM and RMR will be recorded, and muscle strength, and Peak VO₂ will be tested before starting the clinical part. A time schedule for the inclusion visit day will be followed. The participants will meet to their appointment at NIH fasting from midnight. The two first examinations will be RMR and DXA measurements, and both lasts for 30 minutes. The two procedures are performed by qualified personnel at NIH. The next station fasting is blood sampling in the laboratory by a qualified bioengineer. After the blood sampling they will meet for medical interview by the primary investigator, recording ongoing and previous diseases, concomitant and former treatment, inclusion, and exclusion criteria, and signing the informed conscient form. The next step is examination of blood pressure, pulse rate and weight, and the medical session will be finished with handling and the cheese registration form, and their allocated sample of cheese type.

Blood samples will be handled in accordance with the laboratory centre procedures, and the Common Terminology Criteria for Adverse Events (CTCAE) version 4.0 registered. The next step in the program is then lunch and rest for approximately 2 hours.

After lunch they will start with the VO2 tests on treadmill and be sent for the muscular strength tests. Both VO2 test and muscular strength tests will be supervised by qualified master students.

6.2.3 Comparative phase 1:

The XCS will randomly be allocated (1:1) to either daily intake of Jarlsberg cheese or Norvegia cheese. The daily intake of Jarlsberg cheese will be the OED for XCS and the comparative dose of Norvegia. The two cheese doses are nearly equal regarding total energy, protein carbohydrate and fat magnesium and calcium. The trial cheese can be consumed with other food at breakfast, lunch, or other meals during the day. The cheese may also be consumed heated/melted. All participants will be provided vitamin D supplement of $40\mu g/day$. The activity level is continuously recorded in the cheese-supplement – and activity record- form.

The participants meet for blood sampling in week 4 and 8 for measurements of Osteocalcin and Bone Turnover Markers (BTM). At week 8 week a clinical examination with measurement of vital signs and body weight will be performed. Additionally, blood samples will be taken for measurements of biochemical variables and vitamin K₂. The participants will be asked to fill in their diet for four days in the data application created for this study every 8 weeks. The diet registration will be performed and monitored.

6.2.3 Comparative phase 2:

All participants in both groups meet for the new investigation in week 16 and week 24, which is the last visit in the study. In both visits new clinical investigations will be performed with measurement of vital signs and body weight. During the last visit week 24, blood samples will be taken for measurements of Bone specific markers, vitamin K2 and biochemical variables. Sex hormones, muscle strength, Peak VO2 and DXA investigation of BMD,TBS, FFM and LM will be measured at in the same way as at day 0.

CTCAE version 4.0 will be used for registration of AE. In case of AE of grade 3 or 4 according to CTCAE occur for more than three days, the responsible investigator will act. The intake of cheese will be stopped and the XCS will be followed up until the symptoms disappear. The total duration from the last intake of the cheese to the disappearance of the symptoms will be recorded in days together with the treatment procedure. They will be reminded to fill in their dietary record.

6.2.4 Dietary monitoring:

The participants will fill in their dietary intake in an application at baseline and every 8th week of the study. During the last visit an Eating Disorder Examination Questionnaire- Short, derived from EDE-Q © Fairburn and Beglin⁴⁰, will be a part of the interview. The questions will be woven into the anamnestic interview and not as a questionnaire to ensure that the participants do not suffer from disordered eating.

6.3: Treatment administration of the study

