3.2.2: Exclusion criteria.

Active XCS fulfils at least one of the following criteria will be excluded from participation in the study:

- Eating disorder
- Pregnancy
- Known gastrointestinal disorder.
- Abnormal liver or kidney function.
- Diabetes
- Suffering from verified cancer.
- Under systemic treatment with corticosteroids or other immunosuppressive drugs the last 3 weeks before start of the trial treatment.
- Participating in another clinical trial with pharmaceuticals the last six weeks before start of this trial treatment.
- Known milk product allergy.
- Suffering from diseases or injuries that disable them to perform VO2 or muscular strength tests.
- Not able to understand information.
- Do not want or not able to give written consent to participate in the study.

3.3: Recruitment of athletes

The active XCS will be recruited by the primary investigators team and by advertising in social media. They will be recruited from high schools of sports, and cross-country teams and clubs in the area around Oslo. Active XCS fulfils the inclusion and avoid the exclusion criteria will be asked to participate and to give written consent for participation.

IV: Design and randomization

4.1: Study design

The study is performed as an open randomized stratified parallel group design with two strata²⁸. Sex is used as a stratification factor. The two equal sized strata are chosen because of different Optimal Effective Dose (OED) of cheese for women and men, and because the dose-response study previously performed has shown different response in men and women²⁹.

Within each stratum the participants will be allocated into two treatment groups by block randomisation.

4.2: Randomization

The athletes will be randomized (1:1) to either daily intake of Jarlsberg cheese or Norvegia cheese by using block randomization with random block size between 2 and 6^{29} . The daily amount of cheese will be equal in the two cheese-groups with 5 slices (75g) for females and 6 slices (90g) for males.

14.3: Power Analysis

With a significant level of 5%, a power of 90% and a clinically relevant difference in total osteocalcin increase of one-time SD between the two groups, at least 24 XCSs in each group must be included. By correcting for dropouts during the first part of the study, 30 XCS will be included in each group. Totally 60 XCSs will be recruited for participation²⁹.

4.4: Identification of subjects

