Trabecular Bone Score (TBS) will be calculated from the lumbar spine images using TBS iNsight software (Medimaps, Geneva, Switzerland) version 3.0.1. As there is no reference population for TBS in individuals < 40 years, only the absolute values will be used.

Evaluation of the microarchitecture of either tibia or femur neck would give even better information about the bone health of the athletes, and we are looking for possibilities³².

Bodyfat (BF) investigation will be performed. In addition to BMD and TBS, the body composition variables Lean body mass (LM), Bodyfat (BF) and Fat free mass (FFM), will be measured together with RMR, muscle strength and Peak VO2 before starting the clinical part and at the end of the study.

5.4: Muscle strength

Maximal (1 repetition maximum, 1RM) upper body muscle strength will be evaluated by seated pull-down by use of a Technogym Radiant (Technogym, Gambettola, Italy) apparatus and by half-squat performed in a Smith machine (Technogym 2SC multipower, Gambettola, Italy). Test procedure will be initiated by three sets of exercise-specific warm-up with gradually increasing load (ten repetitions at 40%, six repetitions at 60%, and three repetitions at 80% of expected 1RM). The first attempt will be performed with a load approximately 5% below the expected 1RM. After each successful attempt, the load will be increased by 2–5% until the athlete fails to lift the load after 2–3 consecutive attempts. The rest period between each attempt will be 3–4 min. The movement for seated pull-down will start with the handlebar positioned at the same height as the forehead. The athletes must pull the handlebar down to the hip bone. Elbows must be held slightly lateral to simulate a double-poling pull, and the wire must be parallel to the back support on the bench. For the 1RM to be accepted, the handlebar must be pulled completely down in one continuous motion with hands parallel³³.

For half-squat, at the familiarization session, the correct depth (90° knee angle) will be noted for reproduction. The position of the feet will be marked, and the correct depth controlled with an elastic band^{33,34}.

For additional information about changes in muscle mass during the study, lean body mass (LM) will be extracted from the body composition outcomes obtained from the DXA measurement.

5.5: Peak VO₂

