11.2 Statistical methods

The differences between the groups will be considered significant if the p-value is less or equal to 5 %. Comparison between groups regarding assumed continuously distributed variables will be performed by using analyses of covariance (ANCOVA) with a basic observation as covariance and repeated measurements ³⁹. Contingency table analyses will be used for comparison of discrete distributed variables.³⁸. Correlation and regression analysis will be performed to estimate the connection in the development between variables.

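### Day 0 hands out the allocated cheese before the baseline peak VO2 and 1RM tests of an open trial and, separately, lists consent signing after the first study procedures

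*Protocol*

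**What the plan says.** **Order of the visit.** Section 6.2.2 starts with RMR and DXA, then fasting blood sampling, then an interview with the investigator, then blood pressure, pulse and weight. At that point "the medical session will be finished with handling and the cheese registration form, and their allocated sample of cheese type". The text goes on: "The next step in the program is then lunch and rest for approximately 2 hours". Then: "After lunch they will start with the VO2 tests on treadmill and be sent for the muscular strength tests". On who runs the tests it says: "Both VO2 test and muscular strength tests will be supervised by qualified master students". It does not say whether these students know the arm.

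**Openness and analysis.** Section 4.1 says: "The study is performed as an open randomized stratified parallel group design with two strata". The package label in 6.3.2 (Table III) carries the type of cheese. Section 11.2 compares groups by "analyses of covariance (ANCOVA) with a basic observation as covariance and repeated measurements"; I read the basic observation as the baseline value.

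**The strength test.** Section 5.4 sets warm-up loads and a progression: "the load will be increased by 2–5% until the athlete fails to lift the load after 2–3 consecutive attempts". It also has form rules, for example "For the 1RM to be accepted, the handlebar must be pulled completely down in one continuous motion with hands parallel", and squat depth is controlled with an elastic band. It gives no physiological criterion of effort. For peak VO2, 5.5 gives RER and lactate thresholds, with an optional Borg rating.

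**Consent.** Section 6.2.2 puts signing of the consent form in the interview that follows the blood sample. Section 1.6.1, headed Screening, describes a one-week screening and includes candidates who meet the criteria and have signed.

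**The concern.** Peak VO2 and 1RM depend on how hard the athlete tries. If the skier already holds the allocated cheese, expectation can influence the baseline, and ANCOVA carries any arm difference created there into the week-24 comparison. In an open trial, knowing the arm at week 24 cannot be avoided. Knowing it at baseline can: it results only from the order of one visit. Aim 2 in 1.3 compares change in these two variables between the cheeses.

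The consent matter is separate and concerns consistency of the document. Staff who follow 6.2.2 to the letter can scan and sample a skier before a signed form exists; staff who follow 1.6.1 would not. If the form is first signed on Day 0, the clinical screening and the four-day diet registration of the preceding week also come before it.

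**Working it through.** The plan states no figure on this point, so there is none to reproduce.

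**1. Which variables are measured after hand-out?**

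| List | Before hand-out | After hand-out |
|---|---|---|
| Main variables, 1.7 | osteocalcin, bone turnover markers (blood); RMR; BMD (DXA) | none: 0 of 4 |
| Supporting variables, 1.7 | lean mass (DXA); sex hormones (blood) | strength, peak VO2: 2 of 4 |
| Part-2 variables, 5.1 | BMD, RMR | strength, peak VO2: 2 of 4 |

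The sample size (11.3) rests on total osteocalcin, a blood measurement taken before hand-out.

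**2. How open is each test to reduced effort?** Peak VO2 must reach an RER of at least 1.10 and a lactate of at least 7.0 mmol/L (5.5), so a clearly submaximal test would be recognised. The 1RM ends only after 2–3 consecutive failed attempts, with 3–4 minutes of rest between attempts (5.4). That makes an early stop harder, but no measurement separates a true failure from a held-back one. Strength is therefore the main concern.

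**3. How a baseline shift enters the result.** The adjusted difference is (Y1 − Y2) − b(X1 − X2), where Y is the week-24 mean, X the baseline mean and b the ANCOVA slope. If the baseline of one arm is lowered by d, the adjusted difference moves by b × d in favour of that arm.

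**4. Scale only, not an estimate.**
- From 5.4: the load rises by s = 2% to 5% per step. Stopping one step early understates the 1RM by s/(1 + s): 0.02/1.02 = 1.96%, and 0.05/1.05 = 4.76%.
- Assumed: 10% to 33% of one arm stop one step early and nobody in the other arm does; slope b is 0.7 to 1.0.
- Low end: 0.7 × 0.10 × 1.96% = 0.14% of load.
- High end: 1.0 × 0.333 × 4.76% = 1.59% of load.
- If nobody holds back, or both arms do so equally, the shift is zero.

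The protocol gives no SD for 1RM, so these percentages cannot be turned into an effect size or an error rate.

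**5. Consent passages side by side.**
- 1.6.1: signed consent stands under Screening, in the week before Day 0.
- 6.2.2: signing stands in the Day-0 interview, after RMR, DXA and blood sampling.
- 3.3 and 6.2.1: consent is asked for at recruitment, and those willing to sign are enrolled. Neither fixes a signing date.
- 8.3: consent must precede inclusion. Because 6.2.2 treats Day 0 as the inclusion visit, this does not settle the order.
- 1.10: the flow chart marks the criteria at week 0 and has no screening column.

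The discrepancy lies between 1.6.1 and 6.2.2 and concerns when the form is signed.

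**The case against.** On the test order, the case against is that the risk is speculative. No main variable is touched, and peak VO2 is largely protected, which leaves in essence one supporting variable. No direction can be named: both arms receive free cheese at the same dose, with the same stated energy, fat and protein (6.3.1), and equal effects would cancel. Stopping a 1RM test early means failing repeatedly in front of a supervisor. The 0.14% to 1.6% range rests on an assumed share and slope. All of this stands, and it limits the weight of the point. It does not remove the point, because the order serves no stated purpose and changing it costs little.

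On consent, the sentence in 1.6.1 has the same form as 8.3: the signed candidate is included. Taken alone it is no more contradicted by 6.2.2 than 8.3 is. That is fair; the conflict comes from its place under Screening. The Day-0 signing may also be a re-check, though 6.2.2 does not say so.

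A reader might further infer that the eligibility rules contradict each other because criteria are recorded on Day 0. The documents do not support this: recording on Day 0 agrees with the flow chart and is compatible with an earlier check.

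**Conclusion.** The point holds in a limited form and is worth fixing. The order in 6.2.2 lets skiers know their arm before the baseline peak VO2 and 1RM tests. This is an avoidable bias risk of unknown size and direction, mainly for 1RM strength. It rests on reading the covariate in 11.2 as the baseline value and on 6.2.2 being followed as written.

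Three stronger readings should be resisted.
- *Baseline was measured under treatment.* Hand-out is not the start of intake. Section 6.2.2 places the tests before the clinical part, and no passage says when the first portion is eaten.
- *The main comparison is biased.* Every main variable in 1.7 and the sample-size variable are measured before hand-out.
- *The testers are known to be unblinded.* The protocol is silent on this.

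The separate consent point is that 6.2.2 and 1.6.1 differ on when the form is signed. The documents do not show that any participant would in fact have procedures before consent, and 8.3 is not literally contradicted.

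**What to change.** **Test order.** In 6.2.2, disclose the allocation and hand out the cheese only after the VO2 and strength tests are finished on the same day. Hand-out then comes later by about 120 minutes (lunch and rest) + 15 (VO2 warm-up) + 4 to 6 (test) = 139 to 141 minutes, plus the strength session, whose length is not given. Someone must be available at that time, since hand-out now closes the investigator's session. No extra visit or measurement is needed.

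**Consent.** Reconcile 6.2.2 with 1.6.1 so that signed consent is documented before any study procedure, including those of the screening week. If the Day-0 step is a re-check, say so and place it at the start of the visit. The cost is a change of wording and, if the re-check is kept, a few minutes on arrival.

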All the XCS will be given one study identification number of four digits constructed as
follows:Digit 1:Indicate the gender study arm (1=female, 2=male)Digit 2&3:Indicate the athlete number consecutively within each sex arm
(01,02,03 etc.)

V: Evaluation

5.1: Osteocalcin and vitamin K

The main response variable in both the first part of the two sex arms in the study will be tOC, the bone specific markers procollagen (PINP), Collagen (CTX1), Bone specific Alkaline Phosphatase (BALP) and parathyroid hormone (PTH). In the second part of the study, Bone mineral density (BMD) will be the most central variable in addition to Resting metabolic rate (RMR), Muscle strength and peak VO₂. The Osteocalcin ratio R_0 , vitamin K_2 including the different vitamers MK 7, 8, 9 and 9/4H and vitamin K_1 will be used as secondary variables in both study parts.

5.2: Bone specific markers

The bone specific markers investigated in the study are Procollagen (PINP), Collagen (CTX1), Bone specific Alkaline Phosphatase (BALP), Parathyroid hormone (PTH).

5.3: Bone mineral density (BMD)

Participants will be weighed in their underwear, and height will be measured with a fixed stadiometer (Seca scale, Mod: 8777021094, S/N: 587728124885, Seca Deutschland, Hamburg, Germany). A dual energy X-ray absorptiometry (Lunar iDXA, E'CORE Software, version 14.10.022; GE Healthcare, Madison, WI) performing a three-site scan (lumbar area [L2-L4]; femoral neck, trochanter, and shaft [proximal femur]; and whole body compares the bone density with the bone density expected for a healthy adult of the same age, sex and ethnicity as the patient. Total body composition for different necessary measures will be performed. The difference is calculated as a standard deviation (SD) score. The difference between the patient measurement and that of a young healthy adult is known as a T score. The T scores classify as follows:

- above -1 SD is normal.
- between -1 and -2.5 SD is defined as mildly reduced bone mineral density (BMD) compared with peak bone mass (PBM)
- below -2.5 SD is defined as $osteoporosis^{30}$.

The difference between the participants measurement and that of someone of the same age and gender is known as a Z score. A Z-score below -2 indicate a bone density lower than it should be for someone of the participant's age. A Z-score is supposed to be 0, above 0 is very good, below -1 is poor. Z-Score < -1 is recommended further follow-up and clinical examination of secondary risk factors³¹.

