Peak VO2 will be measured by performing a cardiopulmonary exercise test on a treadmill (ELG 90/200 Sports; Woodway, Weil am Rhein, Germany) with an incremental protocol until exhaustion. Gas exchange will be measured using a breath-by-breath gas analysis system (Oxycon Pro analyzer; Jaeger, Würzburg, Germany) with a Hans Rudolph two-way breathing mask (2700 series; Hans Rudolph, Kansas City, KS). Each test is initiated by an individual adjusted warm-up of 15 minutes at 70% of HRmax. The incremental test protocol involves an incline of 10% with individual adjustment of load each minute until reaching exhaustion, resulting in a total duration of about 4-6 minutes with constant load the last minute. Measures of respiratory exchange ratio (RER) \geq 1.10, and lactate concentration \geq 7.0 mmol/L measured 1 min after test termination and analysed immediately in a 1500-Sport-lactate analyser (YSI, Yellow Springs Instruments, Yellow Springs, OH), were required to ensure a valid measure of maximal oxygen uptake (VO₂max). A Borg scale rating \geq 17 may additionally be used to confirm the test result ³⁵.

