6.3.1 Administration and doses

At baseline (week 0) the female and male strata will be provided a cheese sample for 4 weeks consumption of the type of cheese group they are allocated into. The female participants will be provided a sample resembling 75 grams cheese (5 slices) a day, and the male participants

will be provided 90 grams (6 slices) per day. The dose of Jarlsberg and Norvegia cheese is equal, and the dose is fixed due to OED from the former dose-finding study. After 4 weeks all participants will be provided new cheese samples of their study cheese. This will be repeated every 4 weeks till the end of the study at 24 as described previously. The dose of Jarlsberg and Norvegia cheese is equal.

Energy Sources	Jarlsberg Cheese	Norvegia Cheese
Total Energy	1458 kJ (351 kcal)	1458 kJ(351kcal)
fat	27g	27 g
carbohydrates	0 g	0 g
protein	27g	27g
calcium	770mg	820mg
phosphate	550mg	590mg

Tabell II: Cheese Energy Contents per 100 grams

6.3.2 Cheese supply, packing and storage.

The cheese will be delivered in 250-gram packages. The participants will receive the cheese by the investigator every 4 weeks. Both the Jarlsberg- and the Norvegia cheese used in the study will be given free of charge to the participating athletes.

Each package is labelled in accordance with the procedure for clinical trials. Additionally, the participants will be informed on how to perform the intake of the cheese and to store the cheese in a refrigerator at a temperature from 4° to10°C. Expiry date will be printed on the label.

Description	For use only in clinical trial
Trial substance	Type of cheese
Expire date	
Administration	Oral intake
Investigator	
Name of exporter	TINE A/S:
[contact]
Study	Comparative study in Active XCS
EudraCT number	2022-003264-24
Protocol id	XCS-Jarlsberg/IIA
Storage	Refrigerator between 4° to10°C

Table III: Label on each package

6.4: Stopping rule

In case of life-threatening AE or Serious Adverse Events (SAE) occurs, the cheese intake must stop, and the participant treated and followed up in accordance with GP-centre routines.

6.5: Procedures for Blood sampling and analysis.

Blood will be drawn via a cubital vein and separated into serum by centrifugation. Two ml serum will be sent Vitas for Osteocalcin analysis and 2 ml send for K2 analysis at the

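### Nothing in this open trial keeps the testers of 1RM strength and Peak VO2 unaware of the cheese group; the exposure is greatest for 1RM at week 24, and existing staff can reduce it

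*Protocol*

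**What the plan says.** **Openness.** Section 4.1 states: "The study is performed as an open randomized stratified parallel group design with two strata". Masking of a tester or assessor is not described anywhere in the protocol.

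**Who tests.** Section 6.2.2: "Both VO2 test and muscular strength tests will be supervised by qualified master students". For week 24, Comparative phase 2 (the second section numbered 6.2.3) says: "muscle strength, Peak VO2 and DXA investigation of BMD,TBS, FFM and LM will be measured at in the same way as at day 0".

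**Who supplies the cheese.** Section 6.3.2: "The participants will receive the cheese by the investigator every 4 weeks". The package label in Table III has a line for the type of cheese. Under section 5.10, the daily cheese and activity forms are collected by the investigator or the research assistant.

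**Order on Day 0.** In section 6.2.2 the medical session closes with the athlete receiving "their allocated sample of cheese type". Lunch and about two hours of rest follow, then the VO2 and strength tests.

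**How the tests run.** In section 5.4 (1RM), loads start from an expected 1RM and rise in steps of 2–5% until failure over 2–3 consecutive attempts, with rules on when a lift counts. In section 5.5 (Peak VO2), the treadmill test proceeds "with individual adjustment of load each minute until reaching exhaustion". A valid result requires a respiratory exchange ratio of at least 1.10 and lactate of at least 7.0 mmol/L; a Borg rating may be used in addition.

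**Role of the variables.** Aim 2 (sections 1.3 and 2.4) compares the cheeses on these tests. Section 5.1 lists them with the central part 2 variables, next to BMD. Section 1.7 calls them supporting.

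**The concern.** Both tests depend on maximal effort and are run by a person who can encourage the athlete, choose the next load and, for 1RM, accept or reject a lift. If that person knows the cheese group and expects one cheese to do better, the expectation can enter the measurement.

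The protocol supplies a direction for such an expectation. Section 2.1 credits osteocalcin with improving muscular strength, and section 8.1 attributes the osteocalcin effect to components that Jarlsberg has and Norvegia lacks.

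Randomisation does not protect against a bias that arises at measurement. Adjustment for baseline (section 11.2) does not reliably remove it either, because on Day 0 the baseline exercise tests already follow the hand-over of the cheese.

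At stake is the between-group comparison of strength, and to a lesser degree Peak VO2. Section 8.1 links these to whether the cheese could be recommended as prophylaxis.

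**Working it through.** **1. Is tester masking stated or implied?** Sections 1.5 and 4.1 declare the trial open. Sections 5.4, 5.5, 6.2.2 and both sections numbered 6.2.3 describe the tests without restricting what the testers know. So masking is neither stated nor implied. Equally, no section says that the students are told the group.

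**2. Could the testers easily learn the group?** On Day 0, yes. The athlete receives a four-week supply shortly before the tests: 28 × 75 g = 2,100 g for women and 28 × 90 g = 2,520 g for men, in 250 g packs labelled with the cheese type. At week 24 the athlete has eaten a known cheese for the whole study.

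**3. How much discretion does each test leave?**

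| | Tester discretion | Safeguards in the protocol |
|---|---|---|
| 1RM (5.4) | Expected 1RM, steps of 2–5%, 2–3 failed attempts, acceptance of the lift | Fixed warm-up, rest of 3–4 min, bar positions, marked feet, 90° depth controlled with a band; no physiological effort check |
| Peak VO2 (5.5) | Load adjusted each minute | Gas analyser reading; required RER ≥ 1.10 and lactate ≥ 7.0 mmol/L; Borg ≥ 17 only as an addition |

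One more accepted lift moves a 1RM result by 2–5%. Peak VO2 is the less exposed of the two.

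**4. Are testing and cheese supply separate?** The investigator supplies the cheese and the students test, so the roles look separate. The documents do not say whether a student may also be the research assistant who collects the cheese forms.

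**5. Is the study number neutral?** Section 4.4 announces four digits. It defines digit 1 (sex) and digits 2 and 3 (sequence). Digit 4 is not defined in the text available, so neutrality cannot be confirmed.

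**6. Group size.** Section 11.3 gives 24 per group for a 1 SD difference in osteocalcin increase, with 5% alpha and 90% power. By the normal approximation, n = 2(1.960 + 1.282)² / 1² ≈ 21.0, rounded up to 22. The t-test solution is 22.02, so 23. The stated 24 is consistent with this (t-test power 0.924), and 24 / (1 − 0.20) = 30 matches the recruited number. This serves only to set n; it does not bear on the testers.

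**7. Illustration of size.** The documents give no tester bias, so b (in SD units of the outcome) is assumed. With no true cheese effect and an unadjusted two-sided 5% t-test, df = 2n − 2 and the non-centrality is λ = b√(n/2). The false-positive rate is P(|T| > t₀.₉₇₅,df) with T non-central t(df, λ).

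| b (assumed) | λ, n = 24 | Rate, n = 24 | λ, n = 30 | Rate, n = 30 |
|---|---|---|---|---|
| 0 | 0 | 5.0% | 0 | 5.0% |
| 0.1 | 0.35 | 6.3% | 0.39 | 6.7% |
| 0.2 | 0.69 | 10.4% | 0.77 | 11.9% |
| 0.3 | 1.04 | 17.5% | 1.16 | 20.8% |

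The planned analysis is a baseline-adjusted ANCOVA. A smaller residual SD would make the same raw bias weigh more, whereas a bias also present at baseline would be partly adjusted away. The documents give no baseline correlation, so the net effect cannot be computed.

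**The case against.** The strongest reply is that the protocol contains no wrong statement here. It declares an open design, which is understandable for recognisable foods, and it does not say that the students know the group. That stands in part. A reader might infer that the testers are told the allocation, and the documents do not support this; they show only that nothing prevents it. But who may know the allocation at testing is a matter of trial conduct that belongs in the protocol, so a separate SAP would not be expected to settle it.

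Further points on that side:

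- **Safeguards exist.** A reader might treat both tests as equally exposed. The required RER and lactate criteria and the analyser reading speak against that for Peak VO2. For 1RM the technique rules narrow the discretion, and load rises until failure, so part of the choice of step affects resolution only. What remains is encouragement, number of attempts and acceptance of the lift.
- **Rank of the variables.** Sections 1.7 and 5.1 differ, and BMD is named the most central variable in part 2. A reader might extend the point to the main osteocalcin result or the sample size. Osteocalcin is a laboratory assay and is not touched.
- **The size is assumed.** Any assumed bias inflates the error rate, so the table shows sensitivity and is not evidence that a bias exists.
- **Masking testers is only partial.** Athletes know their cheese, and their own effort drives the result. This stands: the change removes one source of bias and leaves another.
- **It is not entirely free.** On Day 0 the order of events or the storage of the cheese must change.

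**Conclusion.** The point holds as a cheap improvement to an open design, strongest for 1RM at week 24. In this trial nothing keeps the students who supervise the 1RM and Peak VO2 tests unaware of the cheese group, and on Day 0 the labelled cheese reaches the athlete before the tests.

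The size is unknown. Under an assumed bias of 0.1 to 0.3 SD and an unadjusted t-test, the false-positive rate would be about 6.3% to 17.5% at 24 per group, or 6.7% to 20.8% at 30 per group, instead of 5%. The conclusion assumes that testers could learn the group and would share the protocol's expectation for Jarlsberg. The documents make both plausible and establish neither. Aim 2 is affected; the osteocalcin comparison and its sample size are not.

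**What to change.** In section 6.2.2 and both sections numbered 6.2.3, state that the existing students who supervise the 1RM and Peak VO2 tests:

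- are not told the allocation;
- take no part in handing out cheese or collecting cheese forms;
- use test sheets that carry only a study number confirmed not to encode the cheese group. Section 4.4 should define digit 4 for this purpose.

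Ask athletes not to mention their cheese to the testers. On Day 0, hand over the cheese after the exercise tests or keep it out of the test area.

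**Cost.** No extra staff are evident from the documents, since supply and testing are already assigned to different roles; the sponsor should confirm that no student doubles as research assistant. Day 0 logistics change slightly. Masking will be imperfect because athletes may disclose their cheese, and their own effort bias remains, which the report should acknowledge.
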